6.2 Dose Modification

6.2.1 Dose-Cohort Study Escalation, Dose Reduction, and Stopping Rules

6.2.1.1 Dose Escalation Scheme

Proposed Dose Escalation Cohort Number	Planned Dose
Dose Level -1	[REDACTED]
Dose Level 1	[REDACTED]
Dose Level 2	[REDACTED]
Dose Level 3	[REDACTED]

Subjects who enter the treatment group in Arm 1 or in Arm 2 will be assigned to the dose level cohort currently open for enrollment for the relevant Arm. Arm 1 and Arm 2 will be enrolled in parallel.

Up to 3 subjects will be enrolled in an initial dose evaluation group and will be treated with NTLA-5001 for Arm 1 and for Arm 2. Enrollment will be staggered as follows (see figure in Section 13.8):

- Staggering of enrollment across the 2 study Arms: Arm 1 and Arm 2 will be escalated independently. If an Arm 1 subject is dosed at a new dose level before an Arm 2 subject, the Arm 1 subject will be observed through Day 28 before dosing a subject in Arm 2.
- Staggering of enrollment within a dose level cohort (either Arm 1 or Arm 2): each of the first 3 subjects will be observed for 28 days before enrolling the next subject.
- Staggering of enrollment between Dose Levels: all subjects in a dose evaluation group will be observed for 28 days before any subject is enrolled at the next Dose Level.

Once the entire dose evaluation group for a study Arm has been observed for 28 days, all data, including DLT information from all cohorts in both Arms, will be reviewed by the Sponsor and treating investigators to consider dose escalation. The following study personnel must participate in review of the study data and dose escalation decision: the Intellia Medical Lead, the Intellia Safety Lead, and any Investigator who has treated a subject in the cohort that has just completed 28-day observation.

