6.2.1.2 Definition of a Dose-limiting Toxicity

DLTs are defined as events with onset within 28 days of infusion as follows:

- Any Grade 4 CRS per American Society for Transplantation and Cellular Therapy (ASTCT) consensus criteria, and Grade 3 CRS that does not resolve to Grade 2 within 72 hours
- Any Grade 3/4 neurotoxicity per ASTCT immune effector cell-associated neurotoxicity syndrome (ICANS) consensus grading criteria for adults
- Any Grade 4 acute GVHD of any duration; Grade 2 or 3 acute GVHD requiring systemic steroid treatment that does not resolve to \leq Grade 1 within 7 days.
- Acute infusion reaction: Reactions related to NTLA-5001 occurring within 2 hours of infusion that are not reversible to \leq Grade 2 within 24 hours.
- Grade 4 neutropenia or thrombocytopenia lasting more than 28 days that is not attributable to underlying disease or lymphodepletion chemotherapy
- Other severe organ toxicity that is not attributable to underlying disease or lymphodepletion chemotherapy as follows: Grade 4 toxicity that is a cardiac disorder, hepatobiliary disorder, renal disorder, respiratory disorder, or vascular disorder (per CTCAE); Grade 3 cardiac, respiratory, or vascular disorder that does not resolve to Grade 2 or lower within 72 hours; or Grade 3 hepatobiliary or renal disorder that does not resolve to Grade 2 or lower within 7 days.
- Grade 5 events without clinical or radiological evidence of disease progression which are related to NTLA 5001.

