6.2.1.3 Dose Escalation and Dose Reduction Decisions

If none of the initial dose evaluation group subjects experience a DLT, subjects in the treatment phase who have not yet received NTLA-5001 and subsequent subjects entering the treatment phase will be eligible for the next dose escalation cohort.

If 1 of the initial dose evaluation group subjects experiences a DLT, enrollment will continue in the dose evaluation group for 3 additional subjects. When the last subject in the expanded dose evaluation group has been observed through Day 28:

- If no subject in the expanded dose evaluation group experiences a DLT, subjects in the treatment phase who have not yet received NTLA-5001 and subsequent subjects entering the treatment phase will be eligible for the next dose escalation cohort.
- If 1 or more additional subject in the expanded dose evaluation group experiences a DLT, no dose escalation will be proposed. Subjects in the treatment phase who have not yet received NTLA-5001 and subsequent subjects entering the treatment phase will be eligible for Dose Level -1 if DLTs are seen at Dose Level 1, or the next lower dose level will be declared the maximum tolerated dose (MTD), if DLTs are seen at Dose Level 2 or 3. Fewer than 2/6 subjects with DLTs will establish the MTD.

If 2 or 3 of the initial dose evaluation group experiences a DLT, no dose escalation will be proposed. Subjects in the treatment phase who have not yet received NTLA-5001 and subsequent subjects entering the treatment phase will be eligible for Dose Level -1 if DLTs are seen at Dose Level 1, or the next lower dose level will be expanded to 6 subjects if DLTs are seen at Dose Level 2 or 3. Fewer than 2/6 subjects with DLTs will establish the MTD.

If a dose escalation is proposed, the subsequent cohort dose may be reduced or increased by up to 50% if the Sponsor and investigator agree, based on observations in the prior cohort. At the Sponsor's discretion, up to 6 subjects may be enrolled in any dose cohort for Arm 1 or Arm 2.

If a subject receiving out-of-specification cells has a DLT, this finding would not be attributed to DLT tally for a specific Dose Level; but would be reviewed as part of the overall safety profile in conjunction with planned safety reviews and by the Sponsor, investigators, and DMC. The event would be considered when making dose escalation decisions, stopping rule decisions, and/or dose selection for expansion cohort.

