6.2.1.4 Simultaneous Escalation of Arm 1 and Arm 2

The risk of severe or serious adverse events after cell therapy is correlated with a subject's tumor burden ([Garcia-Manero et al, 2015](#); [Garzon et al, 2017](#)). Therefore, DLT information from Arm 2 subjects with $\geq 5\%$ bone marrow blasts may inform dose escalation decisions for Arm 1 subjects with $< 5\%$ bone marrow blasts. Simultaneous escalation of Arm 1 and Arm 2 may occur when the following criteria are met:

1. Dose escalation in Arm 2 is recommended from the current dose based on Dose Escalation and Dose Reduction criteria above; and
2. No subjects have experienced DLT at the current dose in Arm 1.

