13.8 Appendix 8 Subject Accrual Order During Dose Escalation

Selected examples shown through dose selection in each Arm. Accrual of six subjects in cohorts prior to expansion is not shown. Each square represents 1 subject with dose level indicated by number. Symbol “*” indicates DLT. Symbol “•” indicates dose escalation decision.

1. No DLT observed

Arm 1	1	1	1	•	2	2	2	•	3	3	3			
Arm 2	1	1	1	•	2	2	2	•	3	3	3			

2. No DLT observed, Arm 1 accrual slower

Arm 1	1	1		•	2			•	3	3		3		
Arm 2	1	1	1	•	2	2	2	•	3	3	3			

3. Single DLT in Arm1, DL2

Arm 1	1	1	1	•	2	2	2*	2	2	2	•	3	3	3
Arm 2	1	1	1	•	2	2		2	•	3	3	3		

4. Single DLT in Arm1 DL2, Arm 1 accrual slower

Arm 1	1	1		•	2*	2	2	2	2	2	•	3		3	3
Arm 2	1	1	1	•	2	2	2	•	3	3	3				

5. Single DLT in Arm 2, DL2

Arm 1	1	1	1	•	2	2	2	•	3	3	3			
Arm 2	1	1	1	•	2	2*	2	2	2	2	•	3	3	3

6. MTD reached in Arm 1, DLT seen in 2/5 subjects at DL2†

Arm 1	1	1	1	•	2	2*	2	2	2*					
Arm 2	1	1	1	•	2		2	2						

7. MTD reached in Arm 2, DLT seen in 2/2 subjects at DL2

Arm 1	1	1	1	•	2	2	2	•	3	3	3			
Arm 2	1	1	1	•		2*	2*							

8. MTD reached in Arm 2, DLT seen in 2/3 subjects at DL2, Arm 1 accrual slower

Arm 1	1			•	2	2		2	•	3	3		3	
Arm 2	1	1	1	•	2*	2	2*							

† In Example #6 above, the MTD for subjects in Arm 1 is reached at a dose lower than the dose under evaluation in Arm 2. Accruing subjects in the order of Example #6 is not expected, because the risk of severe or serious adverse events after cell therapy is correlated with a subject’s tumor burden ([Garcia-Manero et al, 2015](#); [Garzon et al, 2017](#)). If, as in Example #6, the MTD for Arm 1 is reached at or below the dose under investigation in Arm 2, enrollment in Arm 2 will be paused and data reviewed by the Principal Investigators, Sponsor, and the DMC.

DL = dose level; DLT = dose-limiting toxicities; MTD = maximum tolerated dose

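### The prolonged-cytopenia DLT matures too late for the Day 28 escalation decision in the last-dosed subject, and no rule covers an event still open then

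*Protocol*

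**What the plan says.** Protocol Section 6.2.1.2 sets one onset window for every DLT item: "DLTs are defined as events with onset within 28 days of infusion as follows". The blood-count item adds a duration: "Grade 4 neutropenia or thrombocytopenia lasting more than 28 days that is not attributable to underlying disease or lymphodepletion chemotherapy".

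The timing rules in Section 6.2.1.1 are also 28 days. Within a level, "each of the first 3 subjects will be observed for 28 days before enrolling the next subject". Between levels, "all subjects in a dose evaluation group will be observed for 28 days before any subject is enrolled at the next Dose Level". If one of the initial subjects has a DLT, Section 6.2.1.3 says "enrollment will continue in the dose evaluation group for 3 additional subjects", and the next decision comes "When the last subject in the expanded dose evaluation group has been observed through Day 28".

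Section 6.2.1.4 allows Arm 1 to escalate together with Arm 2 on two conditions: Arm 2 escalation is recommended under those same criteria, and "No subjects have experienced DLT at the current dose in Arm 1".

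Neither document says how to treat a Grade 4 cytopenia still running at the decision. The pausing criteria (Section 6.2.1.5) do not list cytopenia. The DLT Evaluable Set (Protocol Table 9-1, SAP Table 2) asks a DLT-free subject to complete Day 29 assessments and sets no condition on an open event. Under the SAP study-day formula, Day 29 is protocol Day 28.

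**The concern.** The escalation rule is a count of DLTs experienced, taken at a fixed time. One of the counted items takes more than 28 days to become a DLT after it starts, and it may start as late as Day 28. For the subject dosed last, the count is closed before this item can be known. Applied to the letter, the omission can only favour escalation, because an open event counts as no DLT.

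Selecting the dose for expansion is the primary objective of the escalation phase (Section 3). The event is also one the protocol watches for. Section 6.7.8 names CD34+ marrow stem cells as a possible on-target site, and Section 8.5.8 lists adverse events attributed to impact on the bone marrow as being of special interest.

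**Working it through.** **1. When the item can be confirmed.** Infusion is Day 0 (Section 4.1). For onset on Day d, a duration of more than 28 days is first reached on Day d+28 if the onset day is counted, or Day d+29 in elapsed days.

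| Onset day | 0 | 7 | 14 | 21 | 28 |
|---|---|---|---|---|---|
| Confirmed, onset day counted | 28 | 35 | 42 | 49 | 56 |
| Confirmed, elapsed days | 29 | 36 | 43 | 50 | 57 |

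At a Day 28 decision, only a Day 0 onset can be confirmed under the first convention and none under the second. The longest wait from Day 28 is 28 or 29 days.

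**2. Which subjects are affected.** The 28-day stagger gives subjects 1, 2 and 3 at least 84, 56 and 28 days of follow-up at the first look. The gap therefore concerns subject 3 (subject 2 only for a Day 28 onset in elapsed days). At the second look subject 3 has at least 56 days. Subjects 4-6 are not staggered, so all three may have only about 28.

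**3. How many are dosed higher meanwhile.** If the next level opens at subject 3's Day 28, its first subject must be observed for 28 days before its second is enrolled: 28 + 28 = Day 56 on subject 3's clock. The event is classified by Day 56/57. So about one subject per escalating arm is dosed before classification.

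**4. Effect on the chance of escalating.** The documents give no rates, so these are assumptions. Let p be the rate of other DLTs, q the rate of cytopenia DLTs (all still open at Day 28 in the subjects named), and r = 1 - (1-p)(1-q).

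- All events counted: (1-r)³ + 3r(1-r)⁵.
- Subject 3 open at the first look, counted at the second: (1-r)²(1-p) + (2r+p)(1-r)⁵.
- Upper bound, subjects 4-6 also open at the second look: (1-r)²(1-p) + (2r+p)(1-r)²(1-p)³.

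For p = 0.10 and q = 0.05, r = 1 - 0.90 × 0.95 = 0.145:

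- All counted: 0.855³ + 3 × 0.145 × 0.855⁵ = 0.625 + 0.199 = 0.824.
- Subject 3 only: 0.855² × 0.90 + 0.390 × 0.855⁵ = 0.658 + 0.178 = 0.836.
- Upper bound: 0.658 + 0.390 × 0.855² × 0.90³ = 0.658 + 0.208 = 0.866.

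| q (p = 10%) | All counted | Subject 3 only | Upper bound | Rise, subject 3 only | Rise, upper bound |
|---|---|---|---|---|---|
| 1% | 0.891 | 0.893 | 0.899 | 0.2 points | 0.8 points |
| 2% | 0.875 | 0.880 | 0.891 | 0.4 points | 1.6 points |
| 5% | 0.824 | 0.836 | 0.866 | 1.2 points | 4.2 points |

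Rises are taken before rounding. At q = 5%, the upper bound is 3.5, 4.2 and 4.2 points for p = 5%, 10% and 20%.

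**5. How often the first look releases the next level with subject 3 open on an event that later qualifies.** This is (1-r)²(1-p)q = 0.7%, 1.4% and 3.3% of cohorts at q = 1%, 2% and 5% (p = 10%). The rise in step 4 is smaller because most of these cohorts would still escalate after expansion. At q = 5%, 3.3% × (1 - 0.855³) = 3.3% × 0.375 = 1.2 points.

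**The case against.** The strongest reply is that the rule is not mechanical. Section 6.2.1.1 has the sponsor's medical and safety leads and the treating investigators review all data, so a running Grade 4 cytopenia would be in front of them. They may wait. Under Section 6.2.1.3 they may enroll up to 6 subjects in a cohort or reduce the next dose by up to half. Section 10 lets the DMC be consulted at any time. Section 2.2.3 reports no cytotoxicity against bone marrow cells in vitro. SAP Section 7 records only 2 treated subjects before termination, so no three-subject decision was affected. All of this stands and limits the weight of the point. It does not close the gap: every safeguard is optional, and two review groups could decide differently on the same data while both follow the protocol.

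Three stronger readings are tempting, and the documents do not support them.

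- *The dose finally chosen is biased.* A subject with a late-confirmed DLT is still evaluable (Section 4.1.1). Later escalation reviews cover DLTs from all cohorts, and the expansion dose is chosen after the DMC reviews all clinical data (Section 6.2.2).
- *Appendix 8 shows Arm 1 escalating on one subject with an unripe event.* In its single-subject cases (example 2 at Dose Level 2, example 8 at Dose Level 1), that subject stands first in the level beside Arm 2's first subject. That implies about 84 days of follow-up. A single Arm 1 subject dosed last is possible, since the examples are only a selection, but it is not what is shown.
- *The chance of escalating is inflated by 10 points or more.* The upper-bound formula gives 18.0 points at a 20% cytopenia DLT rate. Nothing in the documents supports that rate for events not due to leukemia or lymphodepletion.

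**Conclusion.** The point holds as a gap in the rule as written, and it should be fixed. For the last-dosed subject, and for up to three subjects in an expanded group, the cytopenia item cannot inform the escalation decision, apart from a Day 0 onset with the onset day counted. The day arithmetic needs no assumption beyond the counting convention.

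The size is modest: about one subject per escalating arm dosed higher before classification. The 0.2 to 1.2 point rise assumes a 10% other-DLT rate, cytopenia DLT rates of 1% to 5%, independent subjects, every such event in subject 3 still open, and reviewers who apply the count literally. The 0.8 to 4.2 point figures are upper bounds. The final DLT set is not affected. Items qualified by 72 hours or 7 days share the gap only for onsets in the last days of the window.

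**What to change.** In Sections 6.2.1.1 (the between-level bullet), 6.2.1.3 and 6.2.1.4, define a *pending* subject: one with an ongoing Grade 4 neutropenia or thrombocytopenia, or another duration-qualified event, that began within 28 days of infusion and is not attributed to disease or lymphodepletion. Then add:

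- **Escalation.** None, including simultaneous escalation of Arm 1, until the event resolves or meets the DLT definition, unless the decision would be the same with it counted as a DLT.
- **Same-level dosing.** Held only if counting the pending event would give 2 DLTs at that level. Appendix 8 example 7 already stops there: "MTD reached in Arm 2, DLT seen in 2/2 subjects at DL2". A single pending event need not stop dosing, because one DLT does not.
- **Closing rule.** Section 6.6 allows new AML therapy after Day 28, so a hold could otherwise have no end. If the subject dies, has documented progression or starts new AML therapy before classification, the sponsor and treating investigators, with DMC consultation, classify the event on the data up to then. It counts as a DLT for the escalation decision unless it is then attributed to disease or lymphodepletion.
- **Follow-up.** Repeat blood counts until classification. Section 8.4.5 already calls for repeating clinically significant abnormal tests, and the Week 8 visit falls on Day 56.

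The DLT definition, Protocol Table 9-1 and SAP Table 2 stay as they are.

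The cost is wording in three sections and an occasional hold of at most about 28-29 days. In the illustration, a first-look hold for an event that later qualifies occurs in 0.7% to 3.3% of cohorts. Holds for events that later resolve add to this, and the documents give no basis for estimating how many. If the event is confirmed in an otherwise DLT-free initial group, the 3 further subjects are those Section 6.2.1.3 already requires.

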- c. Bone marrow samples collected after the completion of all prior therapy and prior to signing consent are allowed so long as the required bone marrow assessments were completed. Potential Arm 2 subjects: For subjects with $\geq 5\%$ bone marrow blasts, morphology by local assessment is sufficient for eligibility. If a marrow sample collected prior to signing consent is used for enrollment, a bone marrow sampling and PBMC morphology is required between leukapheresis/bridging therapy completion and the initiation of lymphodepleting chemotherapy. Potential Arm 1 subjects: For subjects with $< 5\%$ bone marrow blasts, MRD measurement by the central vendor is needed to determine eligibility. Therefore, a bone marrow sample during screening is required.
- d. Subjects must be reassessed for entry into the study treatment phase within 1 week of lymphodepleting chemotherapy. Please see Section 8.1.3.1
- e. All D0 blood and urine collections should be completed as close as possible to the indicated time.

Table 1-2 Schedule of Activities: Assessment Phase Through End of Study (continued)

Study Period	Assessment Phase							EOS	Notes				
	2	4	8	16	28	40	52			64	76	88	100
Study Week	2	4	8	16	28	40	52	64	76	88	100	112	
Visit Window (days)	±2		±4		±7 days								
Laboratory Assessments (continued)													
vector shedding (urine)	X	X	X	X	X								X
Cytokines (plasma)	X	X	X	X	X								
Cell kinetics	X	X	X	X	X	X	X	X	X	X	X	X	X
PBMC	X	X	X	X	X	X	X	X	X	X	X	X	X
Efficacy Assessments													
Bone marrow sampling and PBMC morphology*	X	X	X	X	X	X	X	X	X	X	X	X	X
Disease response assessment	X	X	X	X	X	X	X	X	X	X	X	X	X
EORTC QLQ-C30	X	X	X	X	X	X	X	X	X	X	X	X	X

*: Includes cytogenetic and molecular profiling and flow cytometry for AML MRD.
 At the investigator's discretion, an early bone marrow aspirate and biopsy may be performed at the Week 2 visit. BM sampling is to be performed until the subject achieves complete remission and has no evidence of MRD. Thereafter, subjects should undergo bone marrow sampling every 12 weeks for 1 year after remission is first documented. Subsequently, subjects in CR are not required to have additional bone marrow sampling unless clinically indicated.
 Refer to Section 13.4 for guidance.

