4.1.1 Replacement of Subjects

An additional subject will be added to a dose cohort if a subject in that cohort does not receive a full dose of NTLA-5001 as per their assigned cohort or fails to complete Day 28 assessments. Any subject who experiences a DLT will be considered evaluable. Data for all subjects will be part of the safety dataset for reporting of the study.

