8.5.3 Criteria for Causal Relationship to the Study Drug

The investigator must provide the causality assessment for an AE. AEs that fall under either "Possible" or "Probable" should be defined as "AEs whose relationship to the study drugs could not be ruled out".

Causal relationship to the study drug	Criteria for Causal Relationship
Not Related	A clinical event, including laboratory test abnormality, with a temporal relationship to drug administration which makes a causal relationship improbable, and/or in which other drugs, chemicals or underlying disease provide plausible explanations.
Possible	A clinical event, including laboratory test abnormality, with a reasonable time sequence to administration of the drug, but which could also be explained by concurrent disease or other drugs or chemicals. Information on drug withdrawal may be lacking or unclear.
Probable	A clinical event, including laboratory test abnormality, with a reasonable time sequence to administration of the drug, unlikely to be attributed to concurrent disease or other drugs or chemicals, and which follows a clinically reasonable response on re-administration (rechallenge) or withdrawal (dechallenge).

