13.4 Appendix 4 Hematological Responses Criteria Definitions

Hematological Response	
CR _{MRD}	Less than or equal to 5% blasts in the bone marrow No evidence of extramedullary disease Full recovery of peripheral blood counts: Platelets > 100,000/ μ l, and ANC > 1,000/ μ l MRD not detected [REDACTED]
CR	Less than or equal to 5% blasts in the bone marrow No evidence of extramedullary disease Full recovery of peripheral blood counts: Platelets > 100,000/ μ l, and ANC > 1,000/ μ l MRD detected [REDACTED]
CRh	Less than or equal to 5% blasts in the bone marrow No evidence of extramedullary disease Partial recovery of peripheral blood counts: Platelets > 50,000/ μ l, and ANC > 500/ μ l
CRi*	Less than or equal to 5% blasts in the bone marrow No evidence of extramedullary disease Incomplete recovery of peripheral blood counts Platelets < 100,000/ μ l or ANC < 1,000/ μ l
MLFS	Less than or equal to 5% blasts in the bone marrow No evidence of extramedullary disease Insufficient recovery of peripheral blood counts: platelets \leq 50,000/ μ l and/or ANC \leq 500/ μ l
Partial Remission (PR)	Bone marrow blasts 6-25% with at least a 50% reduction from baseline
Progressive Disease	An increase from baseline of at least 25% of bone marrow blasts or an absolute increase of at least 5,000 cells/ μ L in the number of circulating leukemia cells
Non-Response	None of the above
Hematological Relapse	Proportion of blasts in bone marrow > 5% or Blasts in peripheral blood after documented CR/CRh/CRi
Extramedullary Disease	
Extramedullary disease	If clinical signs of extramedullary lesions are present, responses are assessed by modified Cheson criteria (Cheson et al, 2007).
Molecular Response	
MRD response	MRD < 0.1% [REDACTED]
MRD complete response	MRD not detected [REDACTED]
MRD relapse	Re-appearance of MRD leukemic cells after MRD complete response

ANC = absolute neutrophil count; CR = complete remission; CRh = complete remission with partial hematologic recovery; CRi = complete remission with incomplete recovery of peripheral blood counts; MLFS = morphologic leukemia-free state; MRD = measurable residual disease; PR = partial remission

* When criteria are met for both CRh and CRi, CRh should be reported. When criteria are met for both CRi and blast-free marrow, CRi should be reported.

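### The Grade 5 DLT criterion leaves out a product-related death whenever progression is present, so the 3+3 count and the Arm 1 escalation test can miss it

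*Protocol*

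**What the plan says.** Protocol 6.2.1.2 defines DLTs as listed events starting within 28 days of infusion. The last bullet, repeated in the synopsis, deals with deaths: "Grade 5 events without clinical or radiological evidence of disease progression which are related to NTLA 5001". It sets two joint conditions: the death is related, and there is no evidence of progression.

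The bullet does not say what counts as progression. Appendix 4 (13.4) has a definition, "An increase from baseline of at least 25% of bone marrow blasts", with an alternative based on circulating leukemia cells, but 6.2.1.2 does not refer to it. Marrow sampling before Week 4 is at the investigator's discretion; the note to Table 1-2 says that "an early bone marrow aspirate and biopsy may be performed at the Week 2 visit".

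On causality, the category Possible in 8.5.3 includes an event "which could also be explained by concurrent disease or other drugs or chemicals", and SAP 6.5.1 treats Possible as related.

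Four rules then depend on whether an event is a DLT:

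- **6.2.1.3 (3+3 rule).** No DLT in the first three subjects permits escalation. One DLT adds three subjects, and a further DLT among them stops escalation. Two or three DLTs stop it at once.
- **6.2.1.4 (simultaneous escalation).** Besides a recommendation to escalate in Arm 2, the only condition is "No subjects have experienced DLT at the current dose in Arm 1".
- **4.1.1 (replacement).** A subject who "fails to complete Day 28 assessments" is replaced, but "Any subject who experiences a DLT will be considered evaluable".
- **DLT Evaluable Set (Protocol 9.3, SAP 4).** A subject without a DLT must complete the Day 29 assessments to be included.

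SAP 6.1 makes DLT incidence the primary endpoint of the escalation phase.

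**The concern.** Relatedness is already a condition of its own, so the progression clause can only remove deaths that were judged related. It removes them because progression is present, not because progression explains the death. In relapsed or refractory AML both can easily be true of one subject. A fatal infection judged possibly related, in a subject with rising blasts, is an example.

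At stake are the escalation count, the Arm 1 test and the reported primary endpoint. The Arm 1 test can rest on very few subjects: Appendix 8 example 2, titled "No DLT observed, Arm 1 accrual slower", shows Arm 1 leaving Dose Level 2 after one subject. An exempted death in a group that small would leave the condition formally met.

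**Working it through.** **Plan's own figures.** The documents give no operating characteristics for the 3+3 rule and no DLT or death rate. The planned maximum of 54 subjects reproduces (2 arms × 3 cohorts × 6 = 36; 2 × 9 = 18; 36 + 18 = 54) and is not affected.

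**Step 1: does another bullet catch the death?** Sometimes. A fatal event that first met the CRS, ICANS, GVHD, infusion-reaction or organ criterion is already a DLT. The organ bullet covers only cardiac, hepatobiliary, renal, respiratory and vascular disorders. A related fatal infection that meets none of these reaches the DLT list only through the Grade 5 bullet.

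**Step 2: compare with the neighbouring bullets.** The cytopenia and organ-toxicity bullets exempt an event only if it is attributable to the leukemia or to lymphodepletion. A Grade 4 renal event not due to AML is therefore a DLT even while blasts are rising. A related fatal infection in the same subject is not.

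**Step 3: follow the exempted death through the rules.** It is not a DLT. If it occurs before Day 28, the subject is replaced under 4.1.1 and is outside the DLT Evaluable Set, so the death leaves both numerator and denominator. In the first three subjects:

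| Events | As written | If the death counts |
|---|---|---|
| The death only | 0/3, escalate | 1/3, add three |
| The death and one other DLT | 1/3, add three | 2/3, no escalation |
| The death only, in Arm 1 (6.2.1.4) | test met | test failed |

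These shifts need no assumed rate.

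**Step 4: size, given that such a death occurs.** Suppose one exempted death among the first three subjects, dosing resumed at the same dose after the pause, and a DLT rate *q* (an assumption) in every other subject.

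- As written, the dead subject is replaced and three evaluable subjects decide: P(escalate) = (1−q)³ + 3q(1−q)²·(1−q)³ = (1−q)³ + 3q(1−q)⁵.
- If the death counts, there is already one DLT, so the other two and the next three must have none: P(escalate) = (1−q)⁵.

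| q | As written | If counted |
|---|---|---|
| 0.10 | 0.729 + 0.3 × 0.590 = 0.906 | 0.590 |
| 0.20 | 0.512 + 0.6 × 0.328 = 0.709 | 0.328 |
| 0.30 | 0.343 + 0.9 × 0.168 = 0.494 | 0.168 |

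**Step 5: size, averaged over whether such a death occurs.** Let T be the true rate of DLTs plus exempted deaths, and e the rate of exempted deaths (both assumptions). With replacement, the rate that the rule sees is (T−e)/(1−e). At T = 0.30, P(escalate) is 0.494 if all are counted. As written it is 0.572, 0.660 and 0.759 for e = 0.05, 0.10 and 0.15. At e = 0.05 the seen rate is 0.25/0.95 = 0.263, and the gap is 0.572 − 0.494 = 0.078.

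Both calculations ignore the pause and the discretionary review.

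**The case against.** The strongest reply is that such a death would not go unseen. Under 6.2.1.5 any treatment-related death suspends enrollment, with no progression exemption, and the sponsor assesses it with the DMC before dosing resumes. Under 6.2.1.1 the first three subjects are staggered by 28 days and all data are reviewed before escalation. The rules in 6.2.1.3 and 6.2.1.4 permit escalation rather than require it. All of this stands and is why the point is minor. But none of these provisions makes the death a DLT, corrects the count or fails the Arm 1 test. For a DLT after out-of-specification cells, 6.2.1.3 says expressly that the event is off the tally but still weighed in escalation decisions. It has no matching sentence for an exempted death.

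Several narrower points also have force:

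- The Not Related category in 8.5.3 can also cover a death that underlying disease plausibly explains. Such a death would fall outside the bullet under either wording. How often a related death coincides with progression cannot be read from the documents.
- The circulating-cell limb of Appendix 4 can be met without a marrow sample, so optional early marrow does not by itself leave progression undefined. The bullet still does not cite Appendix 4.
- SAP 6.5 and 6.5.1 count DLTs on the Safety Analysis Set, so the subject stays in that denominator and the death appears in the AE summaries. The DLT numerator is still one short.
- Arm 1 subjects enter in CR or CRi, which makes evident progression within 28 days less likely there.

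**Conclusion.** The criterion as written can give a wrong count. A death judged related to NTLA-5001, with progression evident and no other bullet met, is not a DLT, and both formal escalation rules miss it. The certain effect is one step in the 3+3 count, or the Arm 1 test read as met when it should fail.

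The probabilities depend on assumed rates. Given such a death, they are 71% against 33% at a 20% DLT rate, 91% against 59% at 10%, and 49% against 17% at 30%. They also require that the pause is lifted and that reviewers follow the count, so they are upper limits on the practical effect. Averaged over whether the death occurs, the gap is smaller: about 8 percentage points at T = 0.30 and e = 0.05.

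The point is minor. Existing safeguards would bring the death to the sponsor and the DMC, and SAP 7 reports that only two subjects received NTLA-5001 before termination. It concerns the rule as written, and any protocol that reuses it, not an escalation that took place.

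**What to change.** Reword the bullet in 6.2.1.2 and in the synopsis to: *Any Grade 5 event related to NTLA-5001, unless the death is clearly attributable to disease progression.* Do not add an exemption for lymphodepletion. The investigator makes and documents the attribution, and it is confirmed in the DMC assessment that the pause already requires.

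Nothing else needs to change. The death becomes a DLT, so under 4.1.1 the subject is evaluable and is not replaced, the DLT Evaluable Set keeps the subject, and the Arm 1 test in 6.2.1.4 fails as it should. An optional addition is to show related deaths and pausing events beside the DLT count, by arm and dose level, at each escalation review. This mostly makes the existing all-data review explicit.

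The cost is one sentence in two places, plus the display if wanted. Attribution calls for a judgement, and confirming it adds a task for the DMC, although clinical evidence of progression is undefined today as well. The DLT rate may look slightly less favourable, and a cohort may be expanded or stopped that would otherwise have escalated. Deaths clearly due to progression stay exempt.
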